1.2. Study Rationale

This study is being conducted to comply with FDA requirements of post-market surveillance of the R3 delta Ceramic Acetabular System.

Smith & Nephew - Advanced Surgical Devices Division

Post-Approval Study of the R3 Biolox delta Ceramic Acetabular System – Europe	Protocol Number: R3H01/02/01/2017/Version2.0
	PMA Number P150030
	ADDENDUM Page: 8 of 25

2. STUDY OBJECTIVES

The primary objective of this phase of this study is to confirm that the safety and effectiveness of the R3 Biolox delta Ceramic Acetabular System (DOD) is maintained in the long term (to 10 years).

2.1. Primary Endpoint

The primary endpoint is implant survivorship at 10 years post study procedure.

The KM survivorship estimate for the DOD group in the PMA cohort at 3 years is 99.3% (95%CI: 97.4%-100.0a). Since this Post-Approval Study (PAS) is intended to document the long-term survivorship of the DOD treatment group only and no comparison to a control is required, no formal statistical hypothesis testing will be conducted.

2.2. Secondary Endpoints

Secondary endpoints include the following:

- Patient outcomes as measured using the modified Harris Hip Score;
- Radiographic evaluation to assess radiographic success defined as:
 - No radiolucencies greater than 2 mm in 50% or more in any of the cup or stem zones; and
 - No femoral or acetabular subsidence greater than or equal to 5mm from baseline; and
 - No acetabular cup inclination changes greater than 4 degrees (4°)

Smith & Nephew - Advanced Surgical Devices Division

Post-Approval Study of the R3 Biolox delta Ceramic Acetabular System – Europe	Protocol Number: R3H01/02/01/2017/Version2.0
	PMA Number P150030
	ADDENDUM Page: 9 of 25

3. STUDY DESIGN

This is a prospective, multicenter, observational study that is currently in the follow-up data collection phase. Five of the seven study sites that contributed data to the PMA cohort will participate in this PAS. The two sites that will not participate in the PAS did not enroll any R3 Biolox delta Ceramic Acetabular System (DOD) PMA subjects, as such their data is not suitable for this PAS. The DOD treatment arm of the PMA Cohort included 137 DOD subjects.

Of the 137 DOD subjects included in the PMA Cohort, one died and one was revised by the 3-year follow-up interval. A total of 135 subjects are therefore eligible for this PAS study and all attempts will be made to continue follow-up on all subjects through the 10-year postoperative interval. Telephone follow-up for determination of device survival or revision status, and patient satisfaction in cases where subjects fail to return for follow-up visits will be conducted.

Smith & Nephew - Advanced Surgical Devices Division

Post-Approval Study of the R3 Biolox delta Ceramic Acetabular System – Europe	Protocol Number: R3H01/02/01/2017/Version2.0
	PMA Number P150030
	ADDENDUM Page: 10 of 25

4. STUDY DEVICE

The R3 delta Ceramic Acetabular System is a ceramic-on-ceramic hip prosthesis composed of modular components that include an R3 porous coated acetabular shell, alumina ceramic acetabular shell liner, an alumina ceramic femoral head, and one of four titanium alloy femoral stems. This acetabular system is used in combination with one of four titanium alloy femoral stems to comprise a total hip replacement. All implantable devices are for single use.

5. STUDY POPULATION

5.1. Subject Enrollment

All study sites and subjects have been recruited and enrollment is closed. DOD cohort subjects that were included in the PMA will continue to be followed as per the follow-up schedule established in the European Post-market Study until they reach the 10-year postoperative interval. Site agreements and signed patient informed consents are already in place and allow for the long-term data collection to 10 years proposed in this PAS.

5.2. Subject Inclusion Criteria

Subjects who met all inclusion criteria and none of the exclusion criteria for inclusion of their records in the PMA Cohort presented in the R3 Biolox Delta Ceramic Acetabular System PMA clinical report (subjects in the DOD treatment arm of the PMA Cohort) will be included in this PAS.

The inclusion criteria for the original European Post-market study are provided below for reference.

- Patient is 18-75 years old and he/she is skeletally mature
- Patient requires primary total hip arthroplasty due to non-inflammatory degenerative joint disease (e.g. osteoarthritis, post-traumatic arthritis, avascular necrosis, dysplasia/ developmental dysplasia of the hip) or inflammatory joint disease (e.g., rheumatoid arthritis)
- Patient has met an acceptable preoperative medical clearance and is free from or treated for cardiac, pulmonary, hematological, etc., conditions that would pose excessive operative risk
- The patient is willing to comply the follow-up schedule

All subjects included in the PMA cohort were required to have signed study informed consent forms, and have device labels confirming the implants used for surgery.

5.3. Subject Exclusion Criteria

Subjects in any of the other treatment arms of the original European Post-market Study are excluded from this PAS.

Smith & Nephew - Advanced Surgical Devices Division

Post-Approval Study of the R3 Biolox delta Ceramic Acetabular System – Europe	Protocol Number: R3H01/02/01/2017/Version2.0
	PMA Number P150030
	ADDENDUM Page: 11 of 25

The exclusion criteria for the original European Post-market study are provided below for reference.

- Patient has active infection or sepsis (treated or untreated)
- Patient is a prisoner or has an emotional or neurological condition that would pre-empt their ability or unwillingness to participate in the study including mental illness, mental retardation, linguistic insufficiencies (i.e. immigrants), or drug/alcohol abuse,
- Patients with acute hip trauma (femoral neck fracture)

Additional exclusion criteria for DOD subjects in the PMA cohort:

- Any subject in the DOD arm who was implanted with any hip system component (other than the ceramic acetabular liner) that is not US FDA 510(k) cleared for use with the study ceramichead.

Smith & Nephew - Advanced Surgical Devices Division

Post-Approval Study of the R3 Biolox delta Ceramic Acetabular System – Europe	Protocol Number: R3H01/02/01/2017/Version2.0								
	PMA Number P150030								
	ADDENDUM Page: 12 of 25								

6. STUDY PROCEDURES

6.1. Study Schematic

The PAS follow-up intervals and schedule of evaluations are provided in Table 1. Data to the 3-year postoperative interval was included in the PMA and is indicated as already collected. Since subjects have already consented to participation to the 10-year interval, data collection is in process and on-going.

Table 1.

Study Activity	Preop	Intra -	D/C	3M	1Y	3Y	5Y (± 6 Mo)	7Y (± 6 Mo)	10Y (± 6
Inclusion/exclusion	Already collected								
Informed consent	Already collected								
Demographics	Already collected								
Modified Harris Hip Score (mHHS)	Already collected					X	X	X	
Radiographic Eval	Already collected					X	X	X	
Adverse Events	Already collected					X	X	X	

6.2. Postoperative 5-, -7, and 10-Year Visits

At the 5-year, 7-year and 10-year postoperative visits subjects will be evaluated using the modified Harris Hip Score (mHHS). The mHHS includes a modification to the “Distance Walked” section of the Harris Hip Score to replace the number of blocks with actual distances since the term “blocks” is not commonly used as a measurement of distance in Europe.

AP and lateral radiographs will be taken at the 5-year, 7-year and 10-year postoperative visits. Radiographs will be evaluated by an independent evaluator according to a Smith & Nephew R3 Acetabular Hip Study Image Evaluation Protocol included in Appendix I.

An adverse event assessment will be conducted at each follow-up interval. Data from each visit will be recorded on the study CRFs (Appendix II).

Smith & Nephew - Advanced Surgical Devices Division

Post-Approval Study of the R3 Biolox delta Ceramic Acetabular System – Europe	Protocol Number: R3H01/02/01/2017/Version2.0
	PMA Number P150030
	ADDENDUM Page: 13 of 25

6.3. Telephone Follow-Up

If subjects are unable to return for follow-up visits to the investigator's office, they may be contacted by telephone to assess their status. Subjects will be asked whether the study device is in place or has been revised, and patient satisfaction will be assessed. This information will be recorded on the corresponding CRF.

Smith & Nephew - Advanced Surgical Devices Division

Post-Approval Study of the R3 Biolox delta Ceramic Acetabular System – Europe	Protocol Number: R3H01/02/01/2017/Version2.0
	PMA Number P150030
	ADDENDUM Page: 14 of 25

7. SUBJECT COMPLETION AND DISPOSITION

7.1. Enrolled Subject

All subjects have been enrolled and signed an EC approved study informed consent that described follow-up to the 10-year postoperative interval. No additional enrollment will occur.

7.2. Conditions for Study Termination

All reasonable efforts should be made to retain the subjects for the 10-year duration of this study. If the subject has a revision of any component, the subject will be terminated from the study.

A. Voluntary Withdrawal

Study participation is voluntary and subjects may withdraw at any point during the study without giving their reason for doing so. A study termination form will be completed for all subjects who do not finish the study, to document the reason for the withdrawal in the CRF.

B. Lost to Follow-Up

Some actively enrolled subjects will not return for follow-up exams due to a variety of reasons. Study personnel will make a reasonable effort to contact the subject and document the following contact attempts prior to declaring a subject to be lost to follow-up: the subject has been contacted according to the study sites policies, but no less than 2 documented phone contacts and 1 certified letter without response. Copies of all attempts to reach the subjects per regular mail or email and/or the attempts to contact the subject via other means should be documented and such documentation should be kept with the subjects CRF. A subject will be considered lost to follow-up if he/she does not appear for the scheduled study visit for 2 consecutive visits and study personnel are unable to contact the subject.

C. Study Termination by Investigator/Sponsor

The Investigator **may** withdraw subjects from the study for many reasons, including but not limited to the following:

- subject noncompliance to study schematic
- subject lost to follow-up

The Investigator **should** withdraw subjects from the study:

- in case any component of the original hardware is revised/exchanged
- if the Investigator or the Sponsor stops the study for any reason

For each case, information will be obtained on the Study Termination Form, detailing circumstances leading to the withdrawal.

D. Study Site Discontinuation

Smith & Nephew - Advanced Surgical Devices Division

Post-Approval Study of the R3 Biolox delta Ceramic Acetabular System – Europe	Protocol Number: R3H01/02/01/2017/Version2.0 PMA Number P150030 ADDENDUM Page: 15 of 25
--	---

A specific study site in this multicenter study may also warrant termination under the following conditions:

- non-compliance to Good Clinical Practice (GCP) or protocol
- major protocol deviations
- inaccurate or incomplete data
- unsafe or unethical practices
- safety or performance considerations
- investigator involuntarily discontinues participation in study

Smith & Nephew - Advanced Surgical Devices Division

Post-Approval Study of the R3 Biolox delta Ceramic Acetabular System – Europe	Protocol Number: R3H01/02/01/2017/Version2.0 PMA Number P150030 ADDENDUM Page: 16 of 25
--	--

8. SAFETY REPORTING

All adverse events, regardless of their relationship to the study device, occurring from the time of study device implantation through to study completion should be recorded on the appropriate CRFs and reported as below.

8.1. Definitions for safety reporting

A. Adverse Event (AE)

An AE is any untoward medical occurrence, unintended disease or injury, or untoward clinical signs (including abnormal laboratory findings) in subjects, users or other persons, whether or not related to the study medical device.

B. Serious Adverse Event (SAE)

A SAE is any adverse event that:

- resulted to death,
- was life threatening (at the time of the event); or
- resulted in hospitalization (initial or prolonged); or
- resulted in a disability or permanent damage (a significant, persistent or permanent change, impairment, damage or disruption in the patient's body function/structure, physical activities and/or quality of life); or
- resulted in a congenital anomaly or birth defect; or
- required medical or surgical intervention to preclude permanent impairment of a body function or prevent permanent damage to a body structure; or
- does not fit the other outcomes above, but may jeopardize the subject and may require medical or surgical intervention (treatment) to prevent one of the other outcomes.

Planned hospitalization for a pre-existing condition, or a procedure required by the protocol, without serious deterioration in health, is not considered a serious adverse event.

C. Unanticipated Serious Adverse Device Effect (USADE)

Any serious adverse effect on health or safety or any life-threatening problem or death caused by, or associated with, a device, if that effect, problem, or death was not previously identified in nature, severity, or degree of incidence in the investigational plan or application (including a supplementary plan or application), or any other unanticipated serious problem associated with the device that relates to the rights, safety, or welfare of subjects.

The Investigator will assess and categorize AEs as mild, moderate or severe based on the following definitions:

- Mild: the subject is aware of the sign or symptom, but finds it easily tolerated. The event is of little concern to the subject and/or little clinical significance. The event is not expected to have any effect on the subject's overall health or wellbeing.

Smith & Nephew - Advanced Surgical Devices Division

Post-Approval Study of the R3 Biolox delta Ceramic Acetabular System – Europe	Protocol Number: R3H01/02/01/2017/Version2.0
	PMA Number P150030
	ADDENDUM Page: 17 of 25

- Moderate: the subject has discomfort enough to cause interference with or change in usual activities. The event is of some concern to the subject's health or wellbeing and may require medical intervention and/or close follow-up.
- Severe: the adverse event interferes considerably with the subject's usual activities. The event is of definite concern to the subject and/or poses substantial risk to the subject's health or well-being. The event is likely to require medical intervention and/or close follow-up and may be incapacitating or life threatening. Hospitalization and treatment may be required.

The Investigator is responsible for assessing the relationship of the AE to the study device and study procedure based on the following definitions:

- Unrelated: the event is clearly not related to the study device or study procedure
- Possible: the event may or may not be related to the study device or study procedure. A relationship cannot be ruled out.
- Probable: the event is likely related to the study device or study procedure. A relationship cannot be ruled out.
- Definite: the event is clearly related to the study device or study procedure.

Smith & Nephew - Advanced Surgical Devices Division

Post-Approval Study of the R3 Biolox delta Ceramic Acetabular System – Europe	Protocol Number: R3H01/02/01/2017/Version2.0
	PMA Number P150030
	ADDENDUM Page: 18 of 25

D. Reoperation and Revisions

A reoperation is any surgical procedure of the study hip. A revision is a surgical procedure of the study hip where one or more of the study components are removed and replaced with new implants.

All reoperations and study component revisions should be documented on the Adverse Event CRF.

8.2. Safety: Investigator's Responsibilities

All reportable adverse events that occur during this follow-up phase should be fully documented in the research record by the Investigator including the onset date, complete description of the event, severity, duration, action taken, and outcome. The event should be documented on the Adverse Event case report form. The investigator will be responsible for notifying the reviewing Ethics Committee, and if applicable other authorities, of any reportable adverse events according to local regulations.

Adverse events which are possibly, probably, or definitely related to the device must be reported promptly to the sponsor. Adverse events which are unanticipated (UADE) must be reported to the sponsor by telephone or by email as soon as possible, and the completed adverse event CRF must be faxed to the Sponsor within 10 working days of gaining knowledge of the event together with a cover letter describing the event and detailing the medical history.

The investigator shall also supply a copy of the completed adverse event investigation form, together with a cover letter describing the event and detailing the medical history to the Ethics Committee. The investigator will also provide any relevant follow-up information and the outcome of the event as soon as possible.

8.3. Safety reporting: Sponsor's Responsibilities

Sponsor will provide progress reports on safety events to the Investigator to report to the EC as required. The Sponsor will also determine whether the risk analysis needs to be updated and assess whether corrective or preventive action is required.

Smith & Nephew - Advanced Surgical Devices Division

Post-Approval Study of the R3 Biolox delta Ceramic Acetabular System – Europe	Protocol Number: R3H01/02/01/2017/Version2.0
	PMA Number P150030
	ADDENDUM Page: 19 of 25

9. STATISTICAL PROCEDURES

9.1. General considerations

General summary statistics for numeric data will include the available records (n), the mean, the standard deviation (SD), the median, the minimum, and the maximum value. For categorical data, the count and percent of data will be presented with the percent based on the number of subjects with data. Implant survivorship will be measured from time of surgery to time of the first instance of removal of any device component for any reason. Subjects who do not experience a removal for any reason will be censored at the date of last data collection. Kaplan-Meier (KM) estimates will be provided by time point (life tables) and graphically (survival curves).

The Statistic Analysis Plan is found in Appendix III.

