7.10 Analysis of Secondary Endpoints

- HOOS sub-scores, HHS (and its subscores) and UCLA would be summarized using descriptive summary characteristics for continuous variables at the preoperative and all postoperative time points. Changes from the preoperative (baseline) to subsequent postoperative visit(s) would also be summarized using descriptive statistics for continuous

CONFIDENTIAL AND PROPRIETARY

This document contains information that is confidential and proprietary to Smith & Nephew PLC and Smith & Nephew, Inc. and is intended for use only by Smith+Nephew and its manufacturer. It shall not be reproduced or copied in whole or in part, nor shall the contents be disclosed by any means without prior written permission from Smith+Nephew, nor shall anyone make any use of it that is contrary to the expressed or implied wishes of Smith+Nephew.

Statistical Analysis Plan

A prospective, multicenter, non-randomized, clinical outcomes study of the R3[◊] Acetabular System in patients with degenerative hip disease

Number:
R3H01/02/01/2017
ST: 1103
Version: 3.0
Page: 16 of 18

variables. Mixed Model Repeated Measures (MMRM) with a missing at random (MAR) assumption to account for the pattern of missing longitudinal data would be used to analyze the Patient Reported Outcome Measures (PROMs) to compare the scores between the preoperative and postoperative visit time points. The model will include fixed effect term for visit. The Kenward Rogers denominator degrees of freedom would be used coupled with a specification for an unstructured covariance matrix. The test of any of the comparisons between the preoperative and postoperative visits will be concluded to be statistically significant if $p < 0.05$. Model-based Means or Least Square (LS) Means for all visits as well as the differences between each postoperative versus the preoperative visit and their 95% two-sided Confidence Intervals (CI) would be presented. Should greater than 10% of any of the PROMs data on at least at two of the postoperative timepoints be missing, MMRM would not be used.

- For radiographic findings, patient satisfaction and Trendelenburg, descriptive summary statistics for categorical variables such as frequency (n) and percentage (%) will be presented by visit.

The secondary endpoint analysis will be performed only on the FAS population.

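### In the DOD post-approval cohort, hips revised for loosening or migration drop out of the radiographic-success percentage instead of counting as failures, overstating it by about 0.7 points per such hip

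*Protocol*

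**What the plan says.** Three parts of the protocol's post-approval addendum combine.

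- **Endpoint (Addendum 2.2).** The secondary endpoints include "Radiographic evaluation to assess radiographic success defined as" three conditions that must all hold. One concerns lucent lines around the implant: "No radiolucencies greater than 2 mm in 50% or more in any of the cup or stem zones; and". Another concerns sinking of either component: "No femoral or acetabular subsidence greater than or equal to 5mm from baseline; and". The third limits the change in cup inclination to 4 degrees. Revision does not appear among the conditions.
- **Follow-up after revision (Addendum 7.2).** "If the subject has a revision of any component, the subject will be terminated from the study". The same section tells the investigator to withdraw a subject "in case any component of the original hardware is revised/exchanged". Films are scheduled at 5, 7 and 10 years (Addendum 6.2), so none is planned after a revision.
- **Denominator (Addendum 9.1).** For categorical data, "the count and percent of data will be presented with the percent based on the number of subjects with data".

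Addendum 9.1 also makes first removal of any component, for whatever reason, the event in the primary survivorship endpoint. Revisions are therefore counted there.

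**The concern.** The radiographic criteria describe failing fixation, and failing fixation is a reason to revise. Section 8.3 of the main protocol itself names aseptic loosening as a possible long-term driver of revision. Removal from the radiographic denominator is therefore informative: some of the hips that leave are the ones the endpoint is meant to detect.

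This has two consequences. A hip that passes at 7 years, loosens at 8 and is revised at 9 is never recorded as a radiographic failure at any visit. A hip that fails at 5 years and is revised at 6 counts against the 5-year rate and then vanishes, so the rate can rise as failures are removed. The addendum's objective is long-term confirmation to 10 years under an FDA approval condition. A radiographic percentage that stays level or improves could be read as stable fixation when it partly reflects which hips are still being filmed.

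**Working it through.** **Reproducing the plan's own figures.** "The DOD treatment arm of the PMA Cohort included 137 DOD subjects" (Addendum 3). One subject died and one was revised by 3 years: 137 − 1 − 1 = 135, the stated number eligible. The stated 3-year survivorship of 99.3% also reproduces as a simple proportion: 1 − 1/137 = 99.27%.

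**Formula.** Let N be the starting hips, r the hips revised after 3 years, k those among r revised for loosening, migration or osteolysis or after a failing film, and s the radiographic successes among unrevised hips.

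- As written: s / (N − r)
- With those k hips kept as failures: s / (N − r + k)
- Gap: [s / (N − r)] × k / (N − r + k). This is zero when k = 0 and positive otherwise (for s > 0), so the error runs in one direction only.

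**Inputs.** N = 135 is from Addendum 3 and 9.2. The documents give neither the number of revisions from 3 to 10 years nor the reasons, so r and k are assumptions shown as a range. Also assumed: about 95% success among unrevised hips, and every unrevised hip filmed. Survivorship is turned into r by counting on 137 and subtracting the one early revision: at 97%, 4 − 1 = 3; at 95%, 7 − 1 = 6; at 90%, 14 − 1 = 13. The 90% is the main study's 10-year hypothesis for the R3 cup, borrowed here only as a low end.

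| Scenario | r | k | As written | Kept as failures | Gap (points) |
|---|---|---|---|---|---|
| No such revision | 0 | 0 | 128/135 = 94.8% | 128/135 = 94.8% | 0 |
| One | 1 | 1 | 127/134 = 94.8% | 127/135 = 94.1% | 0.7 |
| 97% survivorship, all such | 3 | 3 | 125/132 = 94.7% | 125/135 = 92.6% | 2.1 |
| 95% survivorship, all such | 6 | 6 | 123/129 = 95.3% | 123/135 = 91.1% | 4.2 |
| 90% survivorship, about half such | 13 | 6 | 116/122 = 95.1% | 116/128 = 90.6% | 4.5 |
| 90% survivorship, all such | 13 | 13 | 116/122 = 95.1% | 116/135 = 85.9% | 9.2 |

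**Sensitivity.** With 98% success among unrevised hips the gaps barely move: 129/132 = 97.7% against 129/135 = 95.6% (2.2 points) for three hips, and 120/122 = 98.4% against 120/135 = 88.9% (9.5 points) in the extreme row. If the base were 100 hips, one such hip would cost about 1 point (94/99 = 94.9% against 94/100 = 94.0%).

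**Rise over time.** Suppose 3 of 135 hips fail at 5 years, all three are revised before 7 years, and no other hip fails. The rate is 132/135 = 97.8% at 5 years and 132/132 = 100% at 7 years, although no hip improved.

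**The case against.** The strongest reply is that radiographic status among hips still in place, read beside Kaplan-Meier survivorship, is a legitimate pair of results. Survivorship is the primary endpoint and counts every revision, the addendum plans no formal testing, and a hip that fails on film at 5 years does appear in the 5-year table. A composite of film and revision is a different quantity and partly counts the same event twice. This stands as a limit on importance. It does not remove the problem: survivorship pools all reasons for removal and does not isolate fixation failure, and nothing in Addendum 2.2 or 9.1 labels the radiographic percentage as conditional on no revision.

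Two other points stand. Section 9.1 gives a general default, and the addendum refers to its own image-evaluation protocol (Appendix I) and analysis plan (Appendix III). Neither is identifiable in the text available, so a rule for revised hips there cannot be excluded and should be checked first. Also, infection, instability or pain without radiographic failure can lead to revision, and such cases do not inflate the rate in this way.

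The main protocol's statement on multiple imputation (section 9) is not a remedy. It is not carried into the addendum text, SAP 7.10 does not apply it to radiographs, and imputing a film for a removed implant has no clear meaning.

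A reader might extend the point to the whole cohort, because SAP 7.10 plans "For radiographic findings, patient satisfaction and Trendelenburg, descriptive summary statistics for categorical variables" by visit. The documents do not support that step. Withdrawal at revision is stated only in the addendum, section 5.5 of the main protocol has no such rule, and SAP 7.10 sets no denominator for revised hips.

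**Conclusion.** The point holds for the DOD post-approval cohort. On the addendum text, the by-visit radiographic-success percentage is conditional on not having been revised, and any error from this favours the device. The size is about 0.7 points per hip revised for loosening, migration or osteolysis or after a failing film, at N = 135: zero with no such hip, about 2 points for three, 4 to 5 for six, and about 9 in the extreme case. These figures assume about 95% success among unrevised hips and no other attrition.

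A reader might infer that 10-year success will be overstated by up to 10 points, or that the addendum's objective cannot be met. The documents support neither reading. The upper end needs a 90% survivorship that is not a DOD figure, and every revision to be for loosening or migration. With 99.3% survivorship at 3 years the low end, perhaps 0 to 4 points, is more plausible. The objective rests first on survivorship, where these revisions are counted. This is a moderate correction to a descriptive secondary endpoint.

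**What to change.** In Addendum 9.1 and the post-approval analysis, without altering the withdrawal rule:

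- Report radiographic success at 5, 7 and 10 years with hips already revised for loosening, migration/subsidence or osteolysis, or with a failing film before revision, kept in the denominator as failures. Hips revised for other reasons without a failing film stay out.
- Show beside it the percentage among unrevised hips with a film, labelled as such, and the cumulative number of revised hips at each visit.
- Do not carry failing films forward for unrevised hips that are merely lost or whose owners die. Carrying failures but not successes forward would bias the rate downward.
- Take the reason for revision from the event description on the adverse event form (Addendum 8.1 and 8.2). The revision listing in SAP 5.3 covers revisions and components, not reasons. Where the reason is not recorded, show the range from none to all of those revised hips counted as failures.
- State whether the base is 135 or also includes the hip revised by 3 years.

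The cost is a change of wording and one derived flag, with no new visits or films. The downside is a slightly less favourable percentage. Whether the form always captures the reason cannot be confirmed from the text available, which is why the range is needed as a fallback.
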